### Adverse Events of Special Interest (AESIs)

AESIs are immune-related adverse events (irAE) and infusion-related reactions (IRRs). The criteria for classification of an AE as an irAE or IRR are described in [Appendix 1](#) and [Appendix 2](#), respectively.

## 4. ANALYSIS SETS

Data for all patients will be assessed to determine if patients meet the criteria for inclusion in each analysis population prior to releasing the database and classifications will be documented per Pfizer's standard operating procedures.

Only patients who signed informed consent will be included in the analysis sets below.

### 4.1. Full Analysis Set

The FAS will include all patients who receive at least one dose of study drug. Patients will be classified according to the study treatment actually received. If a patient receives more than one treatment the patient will be classified according to the first study treatment received.

### 4.2. Safety Analysis Set

The safety analysis set will include all patients who receive at least one dose of study drug. Patients will be classified according to the study treatment actually received. If a patient receives more than one study treatment, the patient will be classified according to the first study treatment received. In this non-randomized study, the FAS and the safety analysis set are identical.

### 4.3. Other Analysis Set

#### 4.3.1. PK analysis sets

The PK concentration analysis set is a subset of the safety analysis set and will include patients who have at least one post-dose concentration measurement above the lower limit of quantitation (LLQ) for avelumab or axitinib.

The PK parameter analysis set is a subset of the safety analysis set and will include patients who have at least one of the PK parameters of interest for avelumab or axitinib.

#### 4.3.2. Biomarker analysis set

Biomarker analysis set is a subset of the safety analysis set and will include patients who have at least one baseline biomarker assessment. Analysis sets will be defined separately for blood-based and tumor tissue-based biomarkers.

#### 4.3.3. Immunogenicity analysis set

The immunogenicity analysis set is a subset of the safety analysis set and will include patients who have at least one ADA/nAb assessment collected for avelumab.

### 5. GENERAL METHODOLOGY AND CONVENTIONS

#### 5.1. Hypotheses and Decision Rules

##### 5.1.1. Hypotheses and sample size determination

There is no formal hypothesis testing in this study. Approximately 40 patients will be enrolled from each of 2 tumor type cohorts: NSCLC, and UC. Thus, a total of approximately 80 patients will be enrolled. Within each treatment group, ORR will be estimated and the 2-sided exact 95% confidence intervals (CIs) will be calculated.

With 40 treated patients per tumor type cohort, ORR can be estimated with a maximum standard error of 0.079. Further, assuming beta (0.5, 0.5) prior:

- NSCLC Cohort: if 15 responders (out of 40 patients, ORR of 37.5%) are observed, the probability of a true ORR  $\geq 30\%$  (considered a clinically relevant effect above single-agent checkpoint inhibition) will be  $\geq 80\%$  (85.0%).
- UC Cohort: if 19 responders (out of 40 patients, ORR of 47.5%) are observed, the probability of a true response rate  $\geq 40\%$  (considered a clinically relevant effect above single-agent checkpoint inhibition) will be  $\geq 80\%$  (83.4%).

Table 4 provides the exact 95% CI for ORR based on different observed number of responders in a given tumor type cohort.

**Table 4. Sample Size and Exact 95% CI for ORR**

Number of Patients	Number of Responders	Observed ORR	Exact 95% CI for ORR
40	4	10.0%	( 2.8% - 23.7%)
	6	15.0%	( 5.7% - 29.8%)
	8	20.0%	( 9.1% - 35.6%)
	10	25.0%	(12.7% - 41.2%)
	12	30.0%	(16.6% - 46.5%)
	14	35.0%	(20.6% - 51.7%)
	16	40.0%	(24.9% - 56.7%)
	18	45.0%	(29.3% - 61.5%)
	20	50.0%	(33.8% - 66.2%)
	24	60.0%	(43.3% - 75.1%)
	28	70.0%	(53.5% - 83.4%)

CI=confidence interval; ORR=objective response rate.

### **5.1.2. Decision rules**

There are no formal decision rules in this study.

## **5.2. General Methods**

As described in Section 3.4.1, in this study ‘**treatment group**’ (ie, cohort) refers to one of the following:

- NSCLC Cohort: avelumab 800 mg IV Q2W plus axitinib 5 mg PO BID;
- UC Cohort: avelumab 800 mg IV Q2W plus axitinib 5 mg PO BID.

Baseline characteristics, disposition and efficacy data will be summarized based on the FAS by treatment group.

Other safety data, exposure data, concomitant medications and non-drug treatments will be summarized based on the safety analysis set by treatment group.

PK data will be summarized based on the PK analysis set by treatment group and for all treatment groups combined.

Biomarker data will be summarized based on the biomarker analysis set by treatment group.

Immunogenicity data will be summarized based on the immunogenicity analysis set by treatment group and for all treatment groups combined.

### **5.2.1. Data handling after the cut-off date**

Data after the cut-off date may not undergo the cleaning process and will not be displayed in any listings or used for summary statistics, statistical analyses or imputations.

### **5.2.2. Pooling of centers**

In order to provide overall estimates of treatment effects, data will be pooled across centers. The ‘center’ factor will not be considered in statistical models or for subgroup analyses due to the high number of participating centers in contrast to the anticipated small number of patients treated at each center.

### **5.2.3. Presentation of continuous and qualitative variables**

Continuous variables will be summarized using descriptive statistics ie, number of non-missing values and number of missing values [ie, n (missing)], mean, median, standard deviation (SD), minimum, maximum and first and third quartile (Q1 and Q3).

Qualitative variables will be summarized by frequency counts and percentages. Unless otherwise specified, the calculation of proportions will include the missing category. Therefore, counts of missing observations will be included in the denominator and presented as a separate category.

In case the analysis refers only to certain visits, percentages will be based on the number of patients still present in the study at that visit, unless otherwise specified.

#### **5.2.4. Definition of study day**

Start day of study treatment is the day of the first dose of study treatment.

The study day for assessments occurring on or after the start of study treatment (eg, adverse event onset, tumor measurement) will be calculated as:

Study day = Date of the assessment/event - start of study treatment + 1.

The study day for assessments occurring prior to the first dose of study treatment (eg, baseline characteristics, medical history) will be negative and calculated as:

Study day = Date of the assessment/event - start of study treatment.

The study day will be displayed in all relevant data listings.

#### **5.2.5. Definition of start of new anti-cancer drug therapy**

Start date of new anti-cancer drug therapy is used to determine the end of the on-treatment period (see Section [5.2.7](#)).

The start date of new anti-cancer drug therapy is the earliest start date of anti-cancer drug therapy recorded in the 'Follow-up Cancer Therapy' eCRF pages that is after the first dose of study treatment. When start date of anti-cancer drug therapy is missing or partially missing, the imputation rules described in Section [5.3.3.4](#) should be applied using only data from the 'Follow-up Cancer Therapy' eCRF pages.

#### **5.2.6. Definition of start of new anti-cancer therapy**

Start date of new anti-cancer therapy (drug, radiation, surgery) is used for censoring in efficacy analyses (see Section [6.1.1](#) and Section [6.2.2](#)).

The start date of new anti-cancer therapy is the earliest date after the first dose of study treatment amongst the following:

- Start date of anti-cancer drug therapy recorded in the 'Follow-up Cancer Therapy' eCRF pages
- Start date of radiation therapy recorded in 'Concomitant Radiation Treatment', and 'Follow-up Radiation Treatment' eCRF pages with 'Treatment Intent' = 'Curative in intent'
- Surgery date recorded in 'On-Study Anti-Cancer Surgery', and 'Follow-up Anti-Cancer Surgery' eCRF pages when 'Surgery Outcome' = 'Resected' or 'Partially Resected'.

When start date of anti-cancer therapy is missing or partially missing, the imputation rules described in Section [5.3.3.4](#) should be applied using 'Follow-up Cancer Therapy',

‘Concomitant Radiation Treatment’, ‘Follow-up Radiation Treatment’, ‘On-Study Anti-Cancer Surgery’, and ‘Follow-up Anti-Cancer Surgery’ eCRF pages.

### **5.2.7. Definition of on-treatment period**

Safety endpoints will be summarized based on the on-treatment period unless otherwise specified.

On-treatment period is defined as the time from the first dose of study treatment through minimum (30 days + last dose of study treatment, start day of new anti-cancer drug therapy – 1 day).

Safety data collected outside the on-treatment period as described above will be listed and flagged in listings but not summarized.

### **5.2.8. Standard derivations and reporting conventions**

The following conversion factors will be used to convert days into weeks, months or years:  
1 week = 7 days, 1 month = 30.4375 days, 1 year = 365.25 days.

Demographics and physical measurements:

- Age [years]:
  - (date of given informed consent - date of birth + 1) / 365.25
  - In case of missing day, day only: Age [years]: (year/month of given informed consent – year/month of birth)
  - In case only year of birth is given: Age [years]: (year of given informed consent - year of birth)

The integer part of the calculated age will be used for reporting purposes.

For reporting conventions, mean and median should generally be displayed one more decimal place than the raw data and standard deviation should be displayed to two more decimal places than the raw data. Percentages will be reported to one decimal place. The rounding will be performed to closest integer / first decimal using the common mid-point between the two consecutive values. Eg, 5.1 to 5.4 will be rounded to an integer of 5, and 5.5 to 5.9 will be rounded to an integer of 6.

### **5.2.9. Unscheduled visits**

Generally, data collected at unscheduled visits will be included and analyzed for both safety and efficacy analyses in the same fashion as the data collected at scheduled visits except where otherwise noted in the sections that follow. Descriptive statistics (mean, SD, median, minimum, maximum, quartiles) by nominal visit or time point for safety endpoints such as laboratory measurements, ECGs and vital signs will include only data from scheduled visits (if such analyses are performed).

### **5.2.10. Adequate baseline tumor assessment**

Adequate baseline is defined using the following criteria:

- All baseline assessments must be within 31 days prior to and including the date of first dose of study treatment.
- All documented lesions must have non-missing assessments (ie, non-missing measurements for target lesions and non-missing lesions assessment status at baseline for non-target lesions).

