## SCHEDULE OF ACTIVITIES

The schedule of activities table provides an overview of the protocol visits and procedures. Refer to the **STUDY PROCEDURES** and **ASSESSMENTS** sections of the protocol for detailed information on each procedure and assessment required for compliance with the protocol.

The investigator may schedule visits (unplanned visits) in addition to those listed on the schedule of activities table, in order to conduct evaluations or assessments required to protect the well-being of the patient.

Visit Identifiers 	Screening	Study Treatment (1 cycle = 28 days)		End of Treatment/Withdrawal 	Post-Treatment Follow-Up		
		Cycle 1 and higher			Short-Term 	Long-Term 	
		Day 1  (±3 days for cycle ≥2)	Day 15 (±3 days)				
Clinical Assessments							
Informed Consent 	X						
Medical/Oncological History 	X						
Baseline Signs/Symptoms 		X					
Physical Examination 	X	X	X	X	X		
Contraception Check 	X	X	X	X	X		
ECOG Performance Status	X	X	X	X	X		
Vital Signs 	X	X	X	X	X		
Home Blood Pressure Monitoring 		X, continuously monitoring					
Laboratory Studies							
Hematology 	X	X	X	X	X		
Blood Chemistry 	X	X	X	X	X		
Coagulation 	X	X	X	X	X		
Thyroid Function Tests 	X	Cycle 1, then Q8W		X	X		
ACTH 	X	Cycle 1, then Q8W		X	X		
HBV, HCV Tests 	X	If clinically indicated					
Serum/Urine Pregnancy Test( for women of childbearing potential only ) 	X	X		X	X		
Urinalysis 	X	If clinically indicated		X	If clinically indicated		
LVEF by MUGA Scan or Echocardiogram 	X	Cycle 2, then Q12W		X	X (Day 30 only)		
12-Lead ECG 	X	As clinically indicated		X			

Visit Identifiers 	Screening ≤28 Days Prior to Enrollment	Study Treatment (1 cycle = 28 days)		End of Treatment/Withdrawal  Day 30, Day 60, Day 90 (±3 days)	Post-Treatment Follow-Up		
		Cycle 1 and higher			Short-Term 		
		Day 1  (±3 days for cycle ≥2)	Day 15 (±3 days)		Every 12 weeks (±14 days)		
Disease Assessments							
Tumor Assessments 	X	Q8W after first dose of study drug for 1 year from start of study treatment, and then Q12W thereafter until PD regardless of discontinuation of study treatment or initiation of subsequent anti cancer therapy.					

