### **5.1. Allocation to Treatment**

At the time that a patient has signed informed consent and entered screening, the site should contact the interactive response technology (IRT) system to obtain the patient identification number.

Once a patient has met all eligibility criteria, assignment of patient enrollment number, patient enrollment, and allocation of investigational product will be managed by the IRT system. The site will need to contact the IRT system to enroll the patient and to obtain the study drug allocation information. At the time of enrollment, site personnel (study coordinator or specified designee) will be required to enter into or select information from the IRT system including, but not limited to, the user's identification and password, the protocol number, and the patient enrollment number. The IRT system will then provide a treatment assignment and dispensable unit (DU) or vial or bottle number for each investigational product to be dispensed. The IRT system will also provide a confirmation report containing the patient number and DU or vial or bottle numbers assigned. The confirmation report must be stored in the site's files.

Study treatment must be initiated preferably on the day of enrollment, but no later than 3 calendar days after enrollment.

There is a 24 hour a day, 365 days a year IRT helpdesk available for any questions or issues. The study specific IRT reference manual will provide the contact information and further details on the use of the IRT system.

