## 7.6. Tumor Assessments

The decision for body areas to be scanned will depend on the disease under study and the extent of disease. Tumor assessments must include all known or suspected disease sites. The minimum recommended body areas to be scanned depending upon malignancy are detailed in the Imaging Manual.

Baseline scans must be performed within 28 days prior to first dose of study drug.

Anti-tumor activity will be assessed through radiological tumor assessments conducted at baseline, then every 8 weeks from first dose of study drug for 1 year from start of study treatment, and then every 12 weeks thereafter until PD regardless of discontinuation of study treatment or initiation of subsequent anti-cancer therapy, as specified in the [Schedule of Activities](#). In addition, radiological tumor assessments will be conducted whenever PD is suspected (eg, symptomatic deterioration).

The schedule of tumor assessments should be fixed according to the calendar regardless of treatment schedule or treatment delays or interruptions due to toxicity.

Imaging may include chest, abdomen and pelvis computed tomography (CT) or magnetic resonance imaging (MRI) scans.

Brain CT or MRI scans are required at baseline for all patients with stable brain lesions and for those for whom brain metastasis is suspected. If stable brain metastases are present at baseline, brain imaging should be repeated at each tumor assessment. Otherwise, brain imaging will be conducted post- baseline only when clinically indicated.

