#### **9.3.1. Analysis of the Primary Endpoint**

The primary endpoint is confirmed OR based on Investigator assessment per RECIST v1.1.

OR is defined as a CR or PR per RECIST v 1.1 from the first dose of study treatment until disease progression or death due to any cause. Both CR and PR must be confirmed by repeat assessments performed no less than 4 weeks after the criteria for response are first met. ORR is defined as the proportion of patients with a confirmed CR or confirmed PR based on Investigator's assessment per RECIST v 1.1. Confirmed responses are those that persist on repeat tumor assessments for at least 4 weeks after initial documentation or response.

Otherwise, the patient will be counted as a non-responder in the assessment of ORR.

Additionally, patients with inadequate data for tumor assessment (eg, no baseline assessment or no follow-up assessments) will be considered as non-responders in the assessment of ORR. The two-sided exact 95% CIs for ORR will be calculated.

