## RECORDING TUMOR ASSESSMENTS

All sites of disease must be assessed at baseline. Baseline assessments should be done as close as possible prior to study start. For an adequate baseline assessment, all required scans must be done within 28 days prior to treatment and all disease must be documented appropriately. If baseline assessment is inadequate, subsequent statuses generally should be indeterminate.

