### 6.1. Primary Endpoint

#### 6.1.1. Objective response as assessed by the Investigator per RECIST v1.1

##### 6.1.1.1. Primary analysis

The following analyses will be based on the FAS by treatment group. Assessment of response will be made using RECIST v1.1. Assessments below refer to investigator assessment.

**Best overall response (BOR)** will be assessed based on reported overall lesion responses at different evaluation time points from the date of first dose of study treatment until the first documentation of PD, according to the following rules. Only tumor assessments performed on or before the start date of any further anti-cancer therapies will be considered in the assessment of BOR. Clinical deterioration will not be considered as documentation of disease progression.

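### Do the different baseline-scan windows (28 days in the protocol, 31 in the SAP) and stable-disease minimums (8 and 6 weeks) call for a change to the analysis?

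*SAP*

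**What the plan says.** **Baseline window.** The protocol ties the scan to dosing. Section 7.6 states: "Baseline scans must be performed within 28 days prior to first dose of study drug". Footnote 21 of the Schedule of Activities repeats this. Appendix 4 uses the same limit to define adequacy: "For an adequate baseline assessment, all required scans must be done within 28 days prior to treatment". It then gives the consequence: "If baseline assessment is inadequate, subsequent statuses generally should be indeterminate". SAP Section 5.2.10 defines the same term with a longer limit: "All baseline assessments must be within 31 days prior to and including the date of first dose of study treatment".

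**Screening and dosing.** The screening column of the Schedule of Activities counts to a different day, "28 Days Prior to Enrollment", and protocol Section 5.1 allows a short lag after that: "Study treatment must be initiated preferably on the day of enrollment, but no later than 3 calendar days after enrollment".

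**Response.** SAP Section 6.1.1.1 says that best overall response "will be assessed based on reported overall lesion responses at different evaluation time points". These are the investigator's entries. Protocol Section 9.3.1 adds that "patients with inadequate data for tumor assessment (eg, no baseline assessment or no follow-up assessments) will be considered as non-responders".

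**Stable disease.** Appendix 4 requires the SD criteria to be met once, at least 8 weeks after study entry. SAP Section 6.1.1.1 requires at least 6 weeks from first dose.

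**Authority.** Protocol Section 9 and SAP Section 2 both let the SAP modify the protocol's analysis plans. Only major changes to the primary endpoint or its analysis need a protocol amendment.

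**The concern.** Two documents that define the same term should agree, and here a scan 29 to 31 days before first dose is adequate in one and inadequate in the other. The SAP's right to modify the protocol does not obviously settle the matter. The SAP takes responses as reported, and investigators report under Appendix 4. An investigator who judged the baseline too old could mark every later status indeterminate. The SAP would call that patient evaluable, yet the patient would count as a non-responder and might be censored for PFS at first dose. The table of reasons for a non-evaluable best response has a row for no baseline assessment but none for a baseline outside the window, so the cause would not be visible there. The primary endpoint of a 40-patient cohort would then depend partly on site habit.

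The SD minimum looks like the same kind of slip. A first scan done a few days early, within the SAP's tolerance of 7 days, could be SD under one document and not under the other.

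**Working it through.** **1. The plan's own figures.** With n = 40:

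- Maximum standard error = sqrt(0.25/40) = 0.0791 (stated 0.079).
- With a Beta(0.5, 0.5) prior and x responders, the posterior is Beta(0.5 + x, 40.5 − x). For x = 15, P(ORR ≥ 30%) = 84.95% (stated 85.0%). For x = 19, P(ORR ≥ 40%) = 83.37% (stated 83.4%).
- All 11 exact intervals in SAP Table 4 are reproduced.

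**2. The disputed range.** 31 − 28 = 3 days, so scans 29 to 31 days before dosing are at issue (29 to 30 if the dosing day is counted as one of the 31). Screening up to 28 days before enrollment plus up to 3 days to dosing gives 28 + 3 = 31. This is a plausible origin of the SAP's figure, but the SAP does not say so.

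**3. Where the SAP uses its definition.**

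| SAP location | Uses an adequate baseline? |
|---|---|
| 6.1.1.1, best overall response and ORR | No. The only baseline item is the non-evaluable reason for having no baseline assessment |
| 6.2.2.2, duration of response (Tables 5 and 6) | No |
| 6.2.2.4, PFS (Tables 7 and 8) | Yes. Censored at first dose unless death occurs within 16 weeks |

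The examples in protocol 9.3.1 are absent assessments, not late ones. SAP 6.1.1.1 puts that clause into practice without reference to Section 5.2.10.

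**4. The route to ORR.** A response is lost only if all three of these hold: the site breaks the 28-day rule; the investigator then reports the later scans as indeterminate; and the patient would have been a confirmed responder. The second step rests on one sentence in Appendix 4, qualified by the word generally. Neither that appendix's criteria for an indeterminate status nor its Table 9 mentions the age of the baseline scan. If all three hold, one responder is worth 1/40 = 2.5 points:

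| Cohort | Responders | ORR | Exact 95% CI | Posterior probability |
|---|---|---|---|---|
| NSCLC | 15 | 37.5% | 22.7 to 54.2% | 85.0% (ORR ≥ 30%) |
| NSCLC | 14 | 35.0% | 20.6 to 51.7% | 75.9% |
| UC | 19 | 47.5% | 31.5 to 63.9% | 83.4% (ORR ≥ 40%) |
| UC | 18 | 45.0% | 29.3 to 61.5% | 74.3% |

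No step in this chain uses SAP 5.2.10. With 28 days in the SAP, the same patient is lost in the same way. The part of the loss due to the SAP's 31 days is therefore zero.

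**5. PFS, the direct effect.** Take 40 patients with 20 event-free at a landmark: 20/40 = 50.0%. Moving one patient scanned 29 to 31 days before dosing from analyzed to censored at first dose gives:

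- 19/39 = 48.7% if that patient would have been event-free at the landmark;
- 20/39 = 51.3% if that patient would have had an event before it (a death within 16 weeks would still count).

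This is what tightening the SAP to 28 days would do. Under 31 days, such a patient stays in. Even if some statuses were marked indeterminate, documented progression remains progression under Appendix 4 and is an adequate assessment under SAP 5.2.11. Table 7 also counts progression or death within 16 weeks, or after at most one inadequate scan, as an event.

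**6. Stable disease.** SAP 6.2.2.4 puts the first scan at 8 weeks ± 7 days, that is, day 49 to day 63 after first dose (15 days). The SAP minimum is 6 × 7 = 42 days; the Appendix 4 minimum is 8 × 7 = 56 days.

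- If study entry is first dose, days 49 to 55 meet only the SAP rule (7 of 15 days).
- If study entry is enrollment with dosing 3 days later, the protocol limit falls at 56 − 3 = 53 days after dosing, so days 49 to 52 meet only the SAP rule (4 of 15 days).

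These are calendar days, not proportions of patients. A later SD scan, at about week 16, satisfies both rules. Only a patient whose sole SD scan falls in the early days can move out of the SD row. ORR, PFS and duration of response do not use that row.

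**The case for a change.** The strongest argument for acting is that precedence cannot repair data. A status recorded as indeterminate at a site stays so whatever the SAP later calls adequate, and two sites with the same scan could report differently. In an open-label trial it is also better to fix such rules before responses are known, and the cost is a short note. One responder lost at the illustrated thresholds would take the posterior probability below 80% in either cohort.

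Part of this stands. The texts do differ, the visible SAP does not say that either rule is deliberate, and the reported status is what counts. But the argument concerns Appendix 4 and site conduct, not the SAP window, and aligning the two numbers would not remove it. Reporting ORR under both windows would not help either, because a CR or PR that was never reported cannot be restored from reported statuses. The posterior probabilities carry no decision, since SAP Section 5.1.2 sets no formal decision rules. On visibility, SAP Section 6.5.2.2 reports protocol violations that bear on the study's conduct or evaluation. A baseline scan outside the protocol window is a natural candidate, although it is not named there.

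**Conclusion.** No change to the plan is needed. The 28-day rule governs what sites do; the 31-day rule is a tolerance that the analysis applies to PFS. The two can coexist, and the SAP is entitled to set the second. Followed as written, the protocol produces no scans in the disputed range and the difference has no effect. If a few occur, the SAP's version keeps their PFS data, and moving to 28 days would only discard it, shifting an illustrative 50.0% landmark by about 1.3 points per patient in either direction. The effect of the SAP window on ORR is zero. The SD difference is confined to patients whose only SD scan precedes 8 weeks, and the analyst simply applies the SAP's 6 weeks, which accepts every on-schedule first scan.

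This rests on three assumptions. Sites broadly follow the first-dose scan rule; the documents give no count of exceptions. A protocol status of indeterminate is handled as non-evaluable in the SAP. The response rules in SAP 6.1.1.1 are applied as written, without importing the adequate-baseline definition. The SAP's version history is redacted and it cites two administrative change letters that are not among these documents, so whether a reason for either rule was recorded cannot be judged. The conclusion does not depend on it.
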